6.5. Per-protocol Set

The Per-protocol Set will contain all participants who receive all three doses of the study vaccine and provide evaluable samples for analysis of the principal immunological endpoint without any protocol deviation that could lead to its exclusion.

The “principal” immunological analysis will also be performed on the Per-protocol Set if the number of participants in the Per-protocol set differs by more than 5% from the number of participants in the Safety Analysis Set.

7. GENERAL CONSIDERATIONS

The safety and immunogenicity summaries, data listings as well as the statistical analysis of the immunogenicity variables will be the responsibility of the study biostatistician at IQVIA.

7.1. Summary Statistics

For qualitative variables, the population size (N for sample size and n for available data) and the percentage (of available data) for each class of the variable will be presented. Quantitative variables will be summarized using descriptive statistics, including N (with data available, n), mean, standard deviation (SD), coefficient of variation (CV%) as appropriate, median, minimum, and maximum values. Geometric mean will be included for immunogenicity variables, where applicable. Coefficient of variation will not be presented for change from baseline results.

The exact two-sided 95% CIs for a proportion within a treatment group will be calculated using the Clopper-Pearson exact method.

The geometric mean titres (GMTs) or geometric mean concentrations (GMCs) calculations will be performed by taking the anti-log of mean of the log10 titer transformation. Confidence interval for geometric means will be derived by raising 10 to the confidence interval associated with mean of log10 values i.e. CI of geometric mean = $10^{(CI \text{ for the mean of the log10 values})}$. All participants in the analysis set of interest with valid data will be considered. Subjects whose antibody titers/concentrations are below the cut-off of the assay will be given a value of half the cut-off for the purpose of GMT/GMC calculation (i.e., if the titer/concentration value is reported as “ $<X$ ”, $X/2$ will be used).

7.2. Treatment Summarization

In general, data will be presented for each treatment group, with placebo participants from healthy older adult

Document: \\dccar2dnetvnasc01p-lan1.quintiles.net\cp_ops\BIOS\MinervaX\GBS-
NN_NN2\MVX0006\Biostatistics\Documentation\SAP

Author: [REDACTED] Version Number: 1.0

Version Date: 19APR2024

Template No.: CS_TP_BS016 Revision 7

Reference: CS_WI_BS005

Effective Date: 01Nov2021

cohorts (pooled together) and obese and/or diabetic older adult cohorts (pooled together) summarized separately. Data for all study participants combined will also be presented when appropriate. Data summary results will be presented for the following treatment groups as appropriate:

- Healthy Older Adult (HOA) Placebo (Pooled from Cohorts 1 and 2)
- HOA GBS-NN/NN2 50 µg
- HOA GBS-NN/NN2 125 µg
- Obese and/or diabetic Older Adult (O/DOA) Placebo (pooled from Cohorts 3 and 4)
- O/DOA GBS-NN/NN2 50 µg
- O/DOA GBS-NN/NN2 125 µg
- All participants combined, if appropriate

7.3. Precision

Quantitative safety data (clinical laboratory values, vital signs) and immunogenicity data will be reported to the same precision as the source data.

For the reporting of descriptive statistics, the mean, median, standard deviation, and confidence intervals will be presented to one digit more precision than the source data. The minimum and maximum will be presented to the same precision as the source data except for the below precision rules for geometric mean titers (GMT) or concentrations (GMC). Coefficient of variation (%) will always be reported to 1 decimal place. P-values, if any, shall be reported to four decimal places or as <0.0001.

The number of decimals used when displaying GMT or (Geometric Mean Concentrations (GMC) and their confidence limits is shown in the following table:

GMT or GMC Value	Number of decimals to display
<0.1	3
≥0.1 and <10	2
≥10 and <1000	1
≥1000	0

When multiple categories of GMT/GMC values are present in the same table, the number of decimals displayed should match that of the smallest category (i.e. the one with the higher number of decimals). Geometric mean fold ratios (GMFRs) or GMT/GMC ratios and their confidence limits will be displayed with 1 decimal regardless of the actual values.

7.4. Reference Start Date and Study Day

Study Day will be calculated from the reference start date and will be used to show start/stop day of assessments and

Document: \\dccar2dnetvnasc01p-lan1.quintiles.net\cp_ops\BIOS\MinervaX\GBS-NN_NN2\MVX0006\Biostatistics\Documentation\SAP

Author: [REDACTED] Version Number: 1.0

Version Date: 19APR2024

Template No.: CS_TP_BS016 Revision 7

Reference: CS_WI_BS005

Effective Date: 01Nov2021

events. Study day will appear in every listing where an assessment date or event date appears. Reference start date is defined as the day of the first dose of study medication (Day 1 is the day of the first dose of study medication).

- If the date of the event is on or after the reference date, then: Study Day = (date of event – reference date) + 1.
- If the date of the event is prior to the reference date, then: Study Day = (date of event – reference date).

In the situation where the event date is partial or missing, Study Day, and any corresponding durations will appear partial or missing in the listings.

7.4.1. Attributing Events to Vaccine Doses

The dose relative to an event is the most recent study dose given to a subject prior to the start of a given event. For example, if the start date of an AE is between Dose 1 and Dose 2, the relative dose will be Dose 1.

7.5. Baseline

Baseline is defined as the last scheduled non-missing measurement taken prior to dosing and will correspond to Day 1 pre-dose for immunogenicity assessments, clinical laboratory evaluations and vital signs. However, if a subject is missing the planned baseline collection, the previous non-missing scheduled evaluation will become the baseline value.

7.6. Retests, Unscheduled Visits and Early Termination Data

Unscheduled measurements will not be included in summary statistics. Early termination results will be recorded as such and included with the end-of-study summaries.

Listings will include all scheduled, unscheduled, retest and early discontinuation data.

7.7. Common Calculations

For quantitative safety measurements (e.g., vital signs, laboratory evaluations), change from baseline will be calculated as:

- Test Value (after baseline) – Baseline Value

For immunogenicity measurements, fold change from baseline will be calculated as:

- Test Value (after baseline) / Baseline Value

Document: \\dccar2dnetvnasc01p-lan1.quintiles.net\cp_ops\BIOS\MinervaX\GBS-
NN_NN2\MVX0006\Biostatistics\Documentation\SAP

Author: [REDACTED] Version Number: 1.0

Version Date: 19APR2024

Template No.: CS_TP_BS016 Revision 7

Reference: CS_WI_BS005

Effective Date: 01Nov2021

7.8. Software Version

All derivations, statistical analyses, summaries and listings will be generated using SAS version 9.4 or higher (SAS Institute, Inc., Cary, North Carolina).

8. STATISTICAL CONSIDERATIONS

8.1. Missing Data

Missing safety data will not be imputed.

9. OUTPUT PRESENTATIONS

Appendix 1 shows conventions for presentation of data in outputs.

The templates provided with this SAP describe the presentations for this study and therefore the format and content of the summary tables, figures, and listings to be provided by IQVIA Biostatistics.

Some minor modifications may be necessary to the planned design of tables, figures, and listings to accommodate data collected during the actual study conduct.

10. DISPOSITION AND WITHDRAWALS

All subjects who provide informed consent will be accounted for in this study. Subject disposition will be tabulated for each study treatment and for all subjects combined with the number of subjects who are screened, eligible to be randomized, randomly assigned to treatment, complete the study, prematurely discontinue, and the reason for early discontinuation. A listing will present dates of completion or early withdrawal and the reason for early discontinuation, if applicable, for each subject.

Listings of study protocol deviations, study eligibility, treatment randomization, and study treatment administration will be provided.

11. DEMOGRAPHIC AND OTHER BASELINE CHARACTERISTICS

Individual subject demographics and baseline characteristics (medical history and serology screening) will be presented in listings.

Demographic characteristics such as age, sex, race, ethnicity, height, weight, and body mass index (BMI) will be summarized and tabulated by treatment and for all subjects combined. Descriptive statistics will be presented for

Document: \\dccar2dnetvnasc01p-lan1.quintiles.net\cp_ops\BIOS\MinervaX\GBS-
NN_NN2\MVX0006\Biostatistics\Documentation\SAP

Author: [REDACTED] Version Number: 1.0

Version Date: 19APR2024

Template No.: CS_TP_BS016 Revision 7

Reference: CS_WI_BS005

Effective Date: 01Nov2021

age, height, weight, and BMI. Frequency counts and percentages will be presented for sex, race, and ethnicity. No statistical testing will be carried out for demographic or other baseline characteristics.

12. PROTOCOL DEVIATIONS

A deviation from a protocol occurs when Investigator site staff or a study participant does not adhere to the protocol's stipulated requirements, whether inadvertently or planned. Protocol deviations will be listed and will include a classification of critical, minor or major, as determined by Sponsor

Changes to the procedures or events, which may impact the quality of the immunogenicity data, will be considered important/significant protocol deviations and will be described within the clinical study report body text. These changes or events will include any circumstances that will alter the evaluation of the immunogenicity results. Examples include, but may not be limited to, sample processing errors that lead to inaccurate immunogenicity results, and/or inaccurate dosing.

In the case of a important/significant protocol deviation or event, immunogenicity data collected during the affected timepoint will be excluded from the immunogenicity analysis. Other changes to the procedures or events which do not impact the quality of the immunogenicity data will not be considered significant protocol deviations. A common example of a non-significant protocol deviation is a missed blood sample or deviations from blood collection times.

13. MEDICAL HISTORY

Medical history coded using Medical Dictionary for Regulatory Activities (MedDRA) Version 26 or higher will be listed for the safety analysis set.

14. MEDICATIONS

Medication usage will be coded using the WHO Drug Dictionary March 2022 or higher will be presented for the safety analysis set.

- 'Prior' medications are medications which started and stopped prior to the first dose of study medication.
- 'Concomitant' medications are medications which were taken during the treatment period, or specifically:
 - started on or after the first dose of study medication or
 - started prior to the first dose of study medication and were continued after the first dose of study medication

Concomitant medications will be summarized using WHO Drug Class and preferred drug name.

Document: \\dccar2dnetvnasc01p-lan1.quintiles.net\cp_ops\BIOS\MinervaX\GBS-
NN_NN2\MVX0006\Biostatistics\Documentation\SAP

Author: [REDACTED] Version Number: 1.0

Version Date: 19APR2024

Template No.: CS_TP_BS016 Revision 7

Reference: CS_WI_BS005

Effective Date: 01Nov2021

15. STUDY MEDICATION EXPOSURE

Exposure to study medication, as the number of doses administered, will be presented for each treatment group in the Safety Analysis Set.

16. IMMUNOGENICITY ANALYSIS

Listings of blood sample collection date and time for antibody and cellular response will be presented separately for participants within each treatment group. Individual observed values for secondary endpoints will be listed and summarized using descriptive statistics by treatment groups across all scheduled timepoints during the entire study.

The secondary immunogenicity endpoints are antibodies to the four individual AlpS:

- Alp1 antibody concentration in $\mu\text{g/mL}$
- Alp2/3 antibody concentration in $\mu\text{g/mL}$
- Rib antibody concentration in $\mu\text{g/mL}$
- AlpC antibody concentration in $\mu\text{g/mL}$

For each treatment group, at each timepoint that samples are collected for antibody:

- GMCs and their 95% CI will be tabulated (GMC at Day 197 is the “principal” immunological endpoint)
- Geometric mean fold change from baseline with their 95% CI will be tabulated
- Proportion of participants with 4-fold increase from baseline (seroconversion)
- Proportion of participants with antibody concentrations above specific thresholds (1, 2, 4 and 8 $\mu\text{g/mL}$)

Linear mixed model with repeated measures (MMRM) will be used to perform pairwise comparison of the secondary endpoints between treatment groups separately for healthy older adults and obese/diabetic older adults. Results from Days 1, 29, 57, 169 and 197 will be utilized. The model will use fixed effects for treatment, day (as a categorical variable), treatment \times day, and baseline value as a covariate, and a repeated day effect within a subject under an unstructured covariance matrix. Concentration values (i.e., the response variable) will be \log_{10} -transformed prior to the analyses and then back-transformed for presentation. Least-squares adjusted GMC with associated 95% CI for individual treatments and adjusted geometric mean ratio, 95% CI and p-values for pairwise comparison will be presented from the fitted model. Variance between the treatment groups will not be considered equal. Age and sex will be included in the model as covariates. If unstructured covariance matrix leads to model convergence failure, then compound symmetric or auto-regressive AR(1) matrix will be tried in the order mentioned.

Analyses of exploratory endpoints are outside the scope of this plan and will be reported separately from the clinical study report.

Comparative analyses with placebo will be exploratory and should be interpreted with caution considering that there is no adjustment for multiplicity and that treatment group sizes are small for these comparisons.

The immunogenicity analysis will be carried out on the immunogenicity analysis set. The “principal” immunological analysis will also be performed on the Per-protocol Set if the number of participants in the Per-protocol set differs

Document: \\dccar2dnetvnasc01p-lan1.quintiles.net\cp_ops\BIOS\MinervaX\GBS-
NN_NN2\MVX0006\Biostatistics\Documentation\SAP

Author: [REDACTED] Version Number: 1.0

Version Date: 19APR2024

Template No.: CS_TP_BS016 Revision 7

Reference: CS_WI_BS005

Effective Date: 01Nov2021

by more than 5% from the number of participants in the Safety Analysis Set.

The following figures will be produced for the antibody response (secondary endpoints) separately:

- Boxplots of the log10(concentration) per timepoint, stratified by treatment and healthy and obese/diabetic
- Boxplots of the fold-rise from baseline per timepoint, stratified by treatment and healthy and obese/diabetic
- Plots of the LS-adjusted GMCs over time with 95% CIs, stratified by treatment and healthy and obese/diabetic

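### SAP 16 combines arm-specific variances with one baseline slope, so saline placebo can dominate that slope and over-correct the exploratory 125 v 50 µg comparison

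*SAP*

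**What the plan says.** SAP Section 16 plans a mixed model for "pairwise comparison of the secondary endpoints between treatment groups separately for healthy older adults and obese/diabetic older adults". The fixed effects are treatment, day, treatment x day "and baseline value as a covariate, and a repeated day effect within a subject under an unstructured covariance matrix". It adds: "Age and sex will be included in the model as covariates". There is no baseline x treatment or baseline x day term, so one coefficient serves all three arms on all days. On the variances it says: "Variance between the treatment groups will not be considered equal".

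Two further details matter. The SAP says "Results from Days 1, 29, 57, 169 and 197 will be utilized", while Section 7.5 says that baseline "will correspond to Day 1 pre-dose for immunogenicity assessments", so Day 1 is both a response and the covariate. The log10 transformation is stated for the response only: "Concentration values (i.e., the response variable) will be" log10-transformed, with nothing about the scale of the baseline covariate.

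The model supplies the adjusted GMCs, the adjusted ratios and the figure described as "Plots of the LS-adjusted GMCs over time with 95% CIs, stratified by treatment and healthy and obese/diabetic". The descriptive GMCs are calculated without a model (SAP 7.1).

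**The concern.** Placebo is saline (Protocol 6.1), so a placebo recipient's later antibody value should be close to the baseline value: a slope near 1 on the log scale, with small residual variance. The half-cut-off rule in SAP 7.1 reinforces this, because someone below the cut-off at every visit shows no change. After three vaccine doses, a shallower slope and more scatter are plausible.

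With unequal variances, likelihood estimation gives most weight to the arm with least scatter. The placebo slope can then be applied to the vaccine arms, where it may be too steep. This can make the adjusted 125 v 50 µg ratio less precise.

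It can also shift the ratio when baselines differ between dose groups. Randomisation does not protect against such a difference: participants are randomised to vaccine or placebo within a cohort, dose is fixed by cohort, and the cohorts open in sequence (Protocol 4.5, 6.3.2).

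**Working it through.** **Plan's own figures.** Protocol 9.2 gives no power, SD or precision. Its arm sizes reproduce exactly: 30 x 4/5 = 24 and 30/5 = 6; 15 x 4/5 = 12 and 15/5 = 3; 2 x 30 + 2 x 15 = 90. With placebo pooled as in SAP 7.2, the model arms (placebo/50/125) are 12/24/24 in healthy and 6/12/12 in obese/diabetic participants.

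**Formula.** Let β be the true vaccine-arm slope, b the fitted common slope, sx the baseline SD and sv the vaccine residual SD. With complete data the adjusted contrast is (Ȳ125 − Ȳ50) − b(X̄125 − X̄50). For a given b:

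- adjusted variance ∝ sv² + (b − β)²sx²
- unadjusted variance ∝ sv² + β²sx²

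So for b above zero, adjustment loses precision when b > 2β. In a single-day model, each arm's weight in b is proportional to (n − 1)/residual variance if baseline SDs are equal.

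**Single-day example, healthy arms.** Assumed on log10: sx 0.5, sv 0.4, placebo residual SD 0.1, β = 0.3, placebo slope 1.

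- Weights: placebo 11/0.01 = 1100; vaccine 46/0.16 = 287.5.
- Placebo share: 1100/1387.5 = 0.79, from 12 of 60 participants.
- b = 0.79 x 1 + 0.21 x 0.3 ≈ 0.85.
- SE ratio to unadjusted: √[(0.16 + 0.555² x 0.25)/(0.16 + 0.09 x 0.25)] = √(0.237/0.1825) = 1.14.
- Same model with equal variances: placebo share 11/57 = 0.19, b ≈ 0.44, ratio 0.95.

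The loss therefore comes from combining unequal variances with a shared slope.

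**Four post-dose days.** Simulation with arm-specific unstructured covariance, 600 runs per case, the same SDs, Day 1 not a response, and age and sex omitted. The SE of 125 v 50 µg relative to no adjustment was:

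| Vaccine slope β | Healthy: mean b | Healthy: SAP model | Healthy: vaccine-arm slope | Obese/diabetic: SAP model | Obese/diabetic: vaccine-arm slope |
|---|---|---|---|---|---|
| 0 | 0.28 | 1.21 | 1.01 | 1.25 | 1.01 |
| 0.2 | 0.60 | 1.19 | 0.99 | 1.12 | 0.98 |
| 0.3 | 0.71 | 1.10 | 0.95 | 1.10 | 0.94 |
| 0.4 | 0.81 | 1.08 | 0.91 | 1.05 | 0.93 |
| 0.5 | 0.89 | 0.95 | 0.84 | 0.95 | 0.87 |
| 0.7 | 0.94 | 0.76 | 0.75 | 0.76 | 0.75 |

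At β = 0.3 in healthy arms, changing only the placebo SD to 0.05, 0.2 or 0.4 gives 1.19, 1.01 and 0.96. Changing only the baseline SD to 0.3 gives 1.07.

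Separate runs for β of 0.1 to 0.3 gave 1.05 to 1.23 for the SAP model and 0.91 to 1.02 for a vaccine-arm slope. With equal slopes in all arms, the vaccine-arm slope cost about 1%.

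**Shift from baseline imbalance.** Suppose the 125 µg cohort starts 0.15 log10 higher, β = 0.3 and the true ratio is 1.0.

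- Single-day b of 0.85: 10^(−0.555 x 0.15) = 0.83.
- Four-day mean b of 0.71: 10^(−0.41 x 0.15) = 0.87.
- No adjustment: 10^(0.3 x 0.15) = 1.11.

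**The case against.** **The analysis is exploratory.** The protocol tests no hypotheses (9.1) and treats any testing as exploratory and descriptive (9.2). Protocol 9.4.2 mentions mixed models only as an option, for comparisons with placebo, and no stated objective names 125 v 50 µg. All of this stands and limits the consequence. However, the SAP does plan all pairwise comparisons, and its caution about small groups and multiplicity covers only those with placebo.

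**The size rests on assumptions.** This also stands. With vaccine slope 0.1, placebo SD 0.15 and baseline SD 0.5, one check found a common slope of only 0.21 to 0.23 and a loss of 0% to 1%. When the placebo SD approaches the vaccine SD, the pull largely disappears in the healthy arms.

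**No adjustment is not neutral.** The same imbalance moves the unadjusted ratio, in the other direction. That is an argument for a suitable slope rather than for dropping adjustment.

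**Day 1 comes first.** Read literally with a log10 baseline, Day 1 as a response is fitted exactly at slope 1. Its residual variance goes to zero and slope 1 is forced whatever the placebo variance. This is a separate defect, and the calculations above apply once it is repaired. The compound-symmetry and AR(1) fallbacks would still share one slope across arms; they were not simulated.

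**A stronger reading is tempting.** A reader might put b = 1 into the formula and infer a very large loss: at β = 0, √[(0.16 + 0.25)/0.16] = 1.60. The model's fitted slope there averaged 0.28 and the simulated ratio was 1.21. A pull towards exactly 1 also needs a log10 baseline, which the SAP does not state; on a raw scale the pull would be towards whatever the placebo slope is.

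**Conclusion.** The concern holds as a conditional loss of precision and a possible distortion in an exploratory dose comparison. With baseline SD 0.3 to 0.5, vaccine residual SD 0.35 to 0.4 and placebo SD 0.08 to 0.15 (all log10, all assumed), the SE is roughly 5% to 25% larger than unadjusted when the vaccine-arm Day 197 slope is about 0.3 or less, and nearer nil in some combinations. At about 0.5 or more, the SAP model usually still improves on no adjustment, though by less than a vaccine-arm slope would. A slope taken from the vaccine arms does as well or better throughout, apart from about 1% when all slopes are equal.

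A reader might also infer that the principal result is compromised or that baseline adjustment is harmful in general. The documents support neither. The principal Day 197 GMC and the other descriptive summaries (fold change, seroconversion, thresholds) do not use this model, and adjustment with a suitable slope usually helps.

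**What to change.** In SAP Section 16, for each population's model:

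1. Use only Days 29, 57, 169 and 197 as responses, and state that the baseline covariate is log10-transformed.
2. Replace the single baseline term with a baseline x day slope shared by the two vaccine arms, plus one separate slope for placebo that is constant over days.
3. Report LS means and ratios at that population's overall mean log10 baseline.

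This takes one slope to five (4 + 1). It needs no new data and leaves the unequal-variance assumption in place. Because the two vaccine arms share a slope, the 125 v 50 µg ratio does not depend on the reference baseline. Ratios to placebo do, so the reference value should be shown. The vaccine-arm slopes also bear directly on the secondary objective about pre-existing antibody.

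A full baseline x treatment x day term is less suitable. It needs 12 slopes, and with 6 obese/diabetic placebo participants a separate intercept and slope per day leaves residual rank 6 − 2 = 4 for four days. One missing participant would make that covariance matrix singular. Keeping Day 1 as a response would leave the exact fit in place under any of these slopes.

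The cost is a few more parameters and, at worst, a few per cent less precision.
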